2.3 Study setting and cluster design

In the Central Denmark Region, a single Emergency Medical Dispatch Center (EMDC) handles all emergency calls (equivalent to 9-1-1 calls in the US). The region receives approximately 55,000 to 60,000 emergency calls annually and employs around 25 Emergency Medical Service (EMS) Dispatchers, all of whom are either nurses or paramedics. Within the EMDC, EMS dispatchers were divided into one of two clusters, each containing 10 EMS dispatchers. Due to the limited number of clusters, a matched-pair (MP) design was adopted. This design relied on specific criteria for matching, including the average proportion of dispatched urgency levels (with the highest urgency level as the primary criterion), years of employment, and the average call duration. The data used for matching covered a 3-month period from January 1, 2022, to March 31, 2022, both prior to the introduction of video streaming and preceding the pilot phase of the study.

Newly employed personnel where matching was not possible were randomly assigned to one of the two clusters. Before the study period, the implementation of video streaming in the intervention group occurred progressively over a span of 7 months (from June 1, 2022, to December 31, 2022), following a pilot phase that took place from April 19, 2022, to May 31.

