2.4 Endpoints

Primary Outcome Measure

• The frequency of dispatches with the highest level of urgency (A-responses)

Secondary Outcome Measures

- The frequency of dispatches with the levels of urgency A, B, C, D and E,
- Mortality within 30 days after study inclusion,
- Number of participants where the levels of urgency are identical when comparing the ambulance

to and from the scene,

SAP version 1.0: CAM-VISION

- Length of stay at hospital,
- The number of participants needing an ICU admission at hospital,
- Number of emergency calls where the dispatched level of urgency is changed during the call,
- Number of emergency calls where the initially dispatched level of urgency is subsequently lowered,
- Number of emergency calls where the initially dispatched level of urgency is subsequently increased,
- Number of emergency calls where the allocated resources is changed during the call,
- Number of participants readmitted to hospital within 24 hours after a dispatch without hospital admission (lowest level of urgency response level E),
- Duration of emergency medical calls,
- Time from emergency call to dispatch,
- On-scene time

Other Pre-specified Outcome Measures:

- Number of participants with return-of-spontaneous circulation (ROSC) after cardiac arrest
- 90 days neurological outcome after cardiac arrest measured by the cerebral performance scale (CPC)
- 90 days functional outcome after cardiac arrest measured by the modified Rankin Scale (mRS)
- Number of patients with Stroke or TIA identified by the EMS dispatcher in the EMDC
- Rate of revascularization treatment (intravenous thrombolysis and/or endovascular treatment (EVT)) among patients with acute ischemic stroke
- Primary admission to a hospital offering acute stroke treatment
- Onset-to-treatment times for patients with acute ischemic stroke treated with i.v. thrombolysis and onset-to-groin-puncture for patients treated with EVT.
- Number of lowest level of urgency (response level E) dispatched among children (< 15 years

of age)

SAP version 1.0: CAM-VISION

- Re-admissions among children (< 15 years of age) to hospital within 24 hours from a prior emergency call dispatched with lowest level of urgency (response level E)
- Number of dispatches for each level of urgency (response level A, B, C, D and E) among children (< 15 years of age)

3 Study Methods

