3.1 General Study Design and Plan

Study type: Single center, prospective, cluster-randomized, unblinded trial.

Type of Comparison: superiority

Type of control: Matched control group (matched-pair design)

Randomization: Emergency calls received in the Emergency Medical Dispatch Center are allocated

randomly between the intervention group and the control group. Given the extended call duration

within the intervention group, it is anticipated that the control group (telephone-only) will experience

a higher volume of calls.

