3.6 Analysis Populations

Intention to Treat (video stream)

The intention-to-treat populations (intension-to-video-stream) includes all patients allocated to either exposure group. Binary outcomes are investigated using risk differences (RD) implementing linear regression and relative risks (RR) by Poisson regression. Robust variance estimation is applied in both regression analyses. Continuous outcomes are investigated using linear and Tobit regression, where the latter is implemented for time variables that are right censored. Time-to-event variables are SAP version 1.0: CAM-VISION 18.08.2023 Page 6 of 7

investigated using Cox-regression analysis, while CPC and mRS are investigated using ordered logistic regression and by the concordance index. To account for cluster randomization, we will implement cluster robust variance in all regression analyses with a separate cluster id for each EMS dispatcher. Effect measures are presented with 95% confidence intervals and all analyses are conducted in Stata 17.

No per-protocol analyses will be conducted because of substantial risk of selection bias.

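### The call-duration outcome is modelled without the dispatchers' own 2022 call duration, which the trial already holds; if that baseline is predictive, the planned interval is wider than it need be

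*SAP*

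**What the plan says.** - **Design (SAP 2.3).** The text states that "EMS dispatchers were divided into one of two clusters, each containing 10 EMS dispatchers", so there are 20 dispatchers in all. The matching criteria were "the average proportion of dispatched urgency levels (with the highest urgency level as the primary criterion), years of employment, and the average call duration". The window is given as "The data used for matching covered a 3-month period from January 1, 2022, to March 31, 2022", which the same section places before both video streaming and the pilot.
- **Staff without a baseline (SAP 2.3).** "Newly employed personnel where matching was not possible were randomly assigned to one of the two clusters". Their number is not given.
- **Outcome (SAP 2.4).** "Duration of emergency medical calls" is a secondary outcome.
- **Expected direction (SAP 3.1).** The plan already expects longer calls under video: "Given the extended call duration within the intervention group".
- **Model (SAP 3.6).** "Continuous outcomes are investigated using linear and Tobit regression, where the latter is implemented for time variables that are right censored". Variance is cluster-robust with one id per dispatcher, and effects are reported with 95% intervals. No baseline covariate, matching variable or pair term is named there or anywhere else in the SAP. It is not stated whether call duration falls under the linear or the Tobit model.

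**The concern.** The trial holds, for each matched dispatcher, a pre-intervention measurement of the same quantity as the outcome. It used that measurement to form the groups and then leaves it out of the model.

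With 20 dispatchers and many hundreds of calls each, most of the uncertainty in the difference between arms comes from dispatchers being habitually faster or slower. More calls do not reduce that part. A predictive dispatcher-level baseline can.

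The consequence depends on how well duration was matched:

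- **Closely matched:** the estimate is already more stable, but a dispatcher-clustered variance with no pair or baseline term gives no credit for this, so the interval is too wide.
- **Loosely matched or unmatched:** chance differences in usual speed between the two groups of 10 remain as noise. The clustered interval reflects that noise but does not remove it.

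At stake is the precision of the estimated lengthening of calls, which is an operational cost of video that the plan itself anticipates.

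**Working it through.** **The plan's own figure.** Section 3.4 expects 18,000 to 20,000 calls and states no power, effect size, SD or intracluster correlation (ICC). From the annual volume in section 2.3, 55,000 × 4/12 = 18,333 and 60,000 × 4/12 = 20,000, so the figure is reproduced. It is the whole region's volume, including calls to dispatchers outside the study. With 20 of about 25 dispatchers in the study, 18,333 × 20/25 = 14,667 and 20,000 × 20/25 = 16,000, or about 733 to 800 calls each. I use 750.

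**Assumed inputs (not in the SAP).** Dispatcher ICC for call duration: 0.05, with 0.01 as the low end. Correlation ρ between a dispatcher's 2022 and 2023 duration: 0 to 0.7. Degree of matching on duration: none or close.

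**Step 1: share of uncertainty between dispatchers.** Share = ICC / (ICC + (1 − ICC)/750).
- ICC 0.05: 0.05 / (0.05 + 0.95/750) = 97.5%.
- ICC 0.01: 0.01 / (0.01 + 0.99/750) = 88%.

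**Step 2: interval width, adjusted over unadjusted.** The hand approximation is √(1 − ρ²) × 2.110/2.101, where the second factor (1.004) is the change in t quantile from 18 to 17 degrees of freedom. It applies to close matching. Without matching there is a further cost from chance imbalance in the covariate. The last column comes from simulating 20,000 trials per setting on dispatcher means (two-sample t analysis against covariance analysis).

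| ρ | √(1 − ρ²) | Close matching (hand) | No matching (simulated) |
|---|---|---|---|
| 0 | 1.000 | 1.004 | 1.03 |
| 0.3 | 0.954 | 0.958 | 0.99 |
| 0.5 | 0.866 | 0.870 | 0.90 |
| 0.7 | 0.714 | 0.717 | 0.75 |

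The narrowing is therefore 10-13% at ρ = 0.5, 25-28% at 0.7 and 1-4% at 0.3. At ρ = 0 there is a small loss.

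**Step 3: coverage of the planned interval under close matching.** The true SD shrinks by √(1 − ρ²) but the standard error does not, so the effective critical value rises.
- ρ = 0.5: 2.101/0.866 = 2.43, which on 18 degrees of freedom gives about 97.4% (simulated 97.2%).
- ρ = 0.7: 2.101/0.714 = 2.94, about 99.1% (simulated 99.0%).

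**Step 4: adding the covariate to the plain cluster-robust method.** Simulated with the factor J/(J − 1) for J = 20 dispatchers and t on 19 degrees of freedom, ICC 0.01 to 0.05. Adjusted intervals cover about 93-94% when all dispatchers have a baseline, and about 91-93% if 4 new staff (an assumed number) are zero-filled with an indicator. At ICC 0.02, ρ = 0.7 and half the baseline variance matched away, mean width falls from 0.261 to 0.194 call-level SD (ratio 0.74). Coverage moves from 97.0% to 93.5%, so part of that narrowing is under-coverage. A small-sample correction is needed.

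**Step 5: cost of the correction.** For 10 v 10 without a covariate, the bias-reduced variance uses 10/9 in place of 20/19, and t moves from 19 to 18 degrees of freedom: √((10/9)/(20/19)) × 2.101/2.093 = 1.027 × 1.004 = 1.03. The percentages in step 2 compare intervals on the same footing. Against a plain unadjusted interval, a covariate with no predictive value costs up to 1.03 × 1.03 = 1.06. On the same basis the gain is about 7-10% at ρ = 0.5 (0.90 × 1.03 = 0.93; 0.870 × 1.03 = 0.90).

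**The case against.** The strongest reply is that nothing here is wrong. Regression on arm alone with dispatcher-clustered variance estimates the intended difference, and ignoring the matching errs on the safe side. The outcome is one of 13 secondary outcomes, and every size above rests on an ICC and a correlation the SAP does not give. All of this stands. It makes the point an optional gain in precision and makes its size conditional.

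Several stronger readings are tempting and are not supported:

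- **That the call-duration estimate is confounded by dispatcher speed.** Section 3.1 describes a cluster-randomised trial. On that footing, any leftover difference in usual speed is chance imprecision, which the clustered standard error already reflects. Section 2.3 states random assignment explicitly only for new staff, but that is not evidence of systematic imbalance.
- **That the interval is too wide and imbalance also distorts the estimate.** These mostly belong to opposite cases. Close matching leaves little imbalance; loose matching leaves imbalance that the interval already covers.
- **That duration was matched poorly because it is named last.** Section 2.3 ranks only the primary criterion and gives no order for the other two.
- **That a stated amount of power is lost.** The SAP describes a convenience sample with no power target, so there is no benchmark to lose against.
- **That the same covariate should serve the time from call to dispatch.** No baseline for that outcome is described, and call duration is a different quantity.

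It is also fair to object that adding the covariate with plain cluster-robust variance could replace a valid or conservative interval with one that under-covers. Step 4 confirms this, and the fix must deal with it.

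**Conclusion.** The point holds as a conditional gain in efficiency. A pre-intervention value of a secondary outcome was collected and used for matching, and section 3.6 does not use it. If it predicts 2023 duration at dispatcher level with a correlation of about 0.5 or more, the interval can be made about 10-13% narrower at 0.5 and 25-28% narrower at 0.7, with coverage held near 95%. These figures assume 10 v 10 dispatchers, about 750 calls each, ICC 0.05, a linear model and baseline data for every dispatcher. The gain is smaller if several dispatchers lack a baseline and almost nil at a correlation of 0.3. The planned interval is not anti-conservative because of the omission: under close matching it covers about 97-99%. The conclusion is limited to call duration, and the matter is minor.

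**What to change.** In section 3.6, for call duration only:

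1. Add the dispatcher's January to March 2022 average call duration, centred, as a covariate.
2. For new staff with no 2022 value, set the centred value to 0 and include a no-baseline indicator.
3. Keep the dispatcher cluster id, and name a small-sample correction suited to about 20 clusters. One example is a bias-reduced cluster-robust variance with t degrees of freedom equal to the number of dispatchers minus the number of model parameters. State whether the model is linear or Tobit, since the figures above are for the linear case.
4. Report the unadjusted difference alongside.

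The cost is a few lines of SAP text, using data already held from the matching. Section 3.5 says extraction had not begun when the SAP was written, so the covariate could be fixed without knowledge of outcomes; added after results are seen, it would be post hoc. The statistical price is one or two degrees of freedom, and an interval about 1-6% wider if 2022 duration turns out not to predict 2023 duration.

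### The main matching variable, each dispatcher's 2022 A-response share, is left out of the primary model, which costs precision if that share predicts 2023

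*SAP*

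**What the plan says.** SAP section 2.3 describes a matched-pair design with two groups, "each containing 10 EMS dispatchers". The matching criteria are listed as "including the average proportion of dispatched urgency levels (with the highest urgency level as the primary criterion"), followed by years of employment and call duration. On timing: "The data used for matching covered a 3-month period from January 1, 2022, to March 31, 2022", which is before video streaming began. Not everyone could be matched: "Newly employed personnel where matching was not possible were randomly assigned to one of the two clusters".

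The primary outcome in section 2.4 is "The frequency of dispatches with the highest level of urgency (A-responses"). The leading matching variable is therefore the pre-intervention value of the primary outcome.

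Section 3.6 sets out the analysis: "Binary outcomes are investigated using risk differences (RD) implementing linear regression and relative risks (RR) by Poisson regression". On variance it says: "To account for cluster randomization, we will implement cluster robust variance in all regression analyses with a separate cluster id for each EMS dispatcher". Neither there nor elsewhere does the SAP put the 2022 share, another matching variable or a pair indicator into a model.

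**The concern.** Matching on the baseline A-share makes the two arms more alike than two independent sets of ten dispatchers would be. A model with arm as its only term and a dispatcher-clustered variance still treats the 20 dispatchers as independent. If the 2022 share predicts the 2023 share, the estimate varies less from trial to trial than its reported standard error suggests. The interval is then too wide and the test too cautious.

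At stake is power. There are only 20 dispatchers, and section 3.4 calls the sample a convenience sample. A real change in A-responses would be missed more often than necessary, although the covariate has already been derived.

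**Working it through.** **The plan's own figure.** The SAP states no power, effect size or interval width. Its call count reproduces: 55,000 × 120/365 = 18,082 and 60,000 × 120/365 = 19,726, against 18,000–20,000 in section 3.4.

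**Calls per dispatcher.** Section 2.3 says: "The region receives approximately 55,000 to 60,000 emergency calls annually and employs around 25 Emergency Medical Service (EMS) Dispatchers".
- Study period: 18,000/25 = 720 to 20,000/25 = 800; about 750 used.
- Baseline: 55,000/25 × 90/365 = 542 to 60,000/25 × 90/365 = 592; about 560 used.

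**Assumed, not in the SAP.** A-share 40%; between-dispatcher SD 2–5 points; calls per dispatcher with a coefficient of variation of 0.3; random allocation within pairs; either all 20 matched or six unmatched. The planned RD analysis is taken as the usual cluster-robust variance (CR1) with t on 19 df, and the planned RR analysis as CR1 with the normal quantile. Section 3.6 states neither reference.

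**What r requires.** r is the correlation of observed shares, which sampling noise pulls below the true correlation. In squared points, the noise is 2,400/560 × 1.09 = 4.67 in 2022 and 2,400/750 × 1.09 = 3.49 in 2023, where 1.09 = 1 + 0.3². The attenuation factor is the square root of SD²/(SD² + 4.67) × SD²/(SD² + 3.49).
- SD 5: factor 0.86, so r = 0.5 needs a true correlation of about 0.6, and r = 0.7 needs 0.81.
- SD 3.5: factor 0.75, so 0.67 and 0.93.
- SD 2: factor about 0.50, so r = 0.5 needs a true correlation near 1 and r = 0.7 cannot be reached.

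**Approximate width ratio, all matched.** The covariate multiplies the residual SD by √(1 − r²). With 10 equal dispatchers per arm, CR1 understates the SE by √(0.9 × 20/19) = 0.973, which CR2 removes. The quantiles are 2.110 (t, 17 df), 2.093 (t, 19 df) and 1.960.
- RD: (1/0.973) × (2.110/2.093) × √(1 − r²) = 1.036 × √(1 − r²)
- RR, log scale: (1/0.973) × (2.110/1.960) × √(1 − r²) = 1.106 × √(1 − r²)

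Simulation (10,000 trials per setting) agrees closely. Adjusted interval (CR2, t) against planned:

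| r | RD, formula | RD, simulated | RR, formula | RR, simulated | RD, six unmatched | RR, six unmatched |
|---|---|---|---|---|---|---|
| 0 | 4% wider | 4% wider | 11% wider | 11% wider | 4–5% wider | 11–12% wider |
| 0.3 | 1% narrower | 1% narrower | 6% wider | 6% wider | 1% wider | 8% wider |
| 0.5 | 10% narrower | 10–11% narrower | 4% narrower | 4–5% narrower | 5–6% narrower | 1% wider |
| 0.7 | 26% narrower | 27–28% narrower | 21% narrower | 22–23% narrower | 17% narrower | 11% narrower |

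**Covariate alone.** With CR2 and t in both analyses and all matched, the covariate makes the interval under 0.5% wider at r = 0, then 5%, 13–14% and 30% narrower at r = 0.3, 0.5 and 0.7. With six unmatched the figures are under 1% wider, then 3%, 9% and 20% narrower.

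**Coverage of the planned intervals, all matched.**

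| r | RD | RR |
|---|---|---|
| 0 | 93.8–94.3% | 92.2–92.7% |
| 0.3 | 94.8–95.0% | 93.3–93.5% |
| 0.5 | 96.5–96.7% | 95.3–95.7% |
| 0.7 | 98.4–98.6% | 97.9% |

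The planned RR interval is thus somewhat too short when the baseline predicts poorly and too wide when it predicts well. The adjusted analysis covers 94.2–95.1% throughout. Adding the covariate but keeping CR1 covers only 91.6–93.5% (RD) and 89.6–91.8% (RR).

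**Power.** Where the adjusted analysis has 80%, the planned RD test has 72–73% (r = 0.5) or 54–55% (r = 0.7) with all matched, and 76–77% or 67–68% with six unmatched. The planned RR test, all matched, has 77% or 60–62%.

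**Bias.** A second simulation, with other call counts and r as the true correlation, kept the mean RD within 0.2 points of zero in every setting and analysis. At SD 5 and a true correlation of 0.8, the unadjusted estimate had an SD of 1.70 points against a mean reported SE of 2.28.

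**The case against.** The planned analysis is valid: matching in the design and analysing without the pairs is permissible, and the cost is at worst a conservative interval. That stands, and it is why this is a point about precision.

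The gain rests on quantities the SAP does not give. This also stands. By true correlation, with all matched, adjusted RD intervals run from 0.5% wider to 7% narrower at 0.5, 3–18% narrower at 0.7 and 7–31% narrower at 0.85. The largest figures are a favourable case.

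Pairing all 20 on A-share alone is a best case too. Section 2.3 also uses employment and call duration, some staff were unmatched, and the exclusions in section 3.2 may break pairs. With ten unmatched, the RD gain falls to 2.5% at r = 0.5 and 10% at r = 0.7. Looser pairing on a composite key does not remove it. Planned RD coverage is then near nominal (95.2% at r = 0.5), but the estimate itself gains (SD 7% and 20% lower at r = 0.5 and 0.7) and the interval is still 9% and 26% narrower.

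The remedy also changes the variance method. That is true and necessary, since the covariate with CR1 under-covers; the two effects are shown separately above.

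Finally, the absence of bias assumes random allocation within pairs, and section 2.3 says only that dispatchers were divided. That caveat stands.

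**Conclusion.** The concern holds as a matter of precision. The design uses the baseline value of the primary outcome and the analysis does not. If observed 2022 and 2023 shares correlate at about 0.5 or more, the planned RD interval is wider than it need be: by the figures above, adjustment would take off roughly 5–11% at r = 0.5 and 17–28% at r = 0.7, depending on how many dispatchers were matched. At 0.3 or below there is essentially no gain for RD, and RR pays for its small-sample correction. With close matching, the point estimate changes little: its SD falls by only about 2% at r = 0.5 and 6% at r = 0.7. What is lost is mainly credit for the balance in the interval and test.

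Confidence is medium, because the A-share, between-dispatcher SD, correlation and number unmatched are all assumed. At r = 0.5, A-shares of 25% or 55% (SD 5) still gave an 11% narrower RD interval. So did 20–50% more calls in the control arm (SD 3.5).

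**What to change.** In section 3.6, prespecify for the primary outcome:

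- the planned call-level RD and RR models, adjusted for the dispatcher's January–March 2022 A-share;
- a missing-baseline indicator for dispatchers without 2022 data;
- a CR2 cluster-robust variance by dispatcher, with a t reference on dispatchers minus parameters (20 − 3 = 17 df, or 16 with the indicator);
- the unadjusted model as a sensitivity analysis.

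The covariate should not be added with the usual sandwich variance alone. For RD the correction is easy to run. All terms are constant within a dispatcher, so the model equals a call-weighted regression on 20 dispatcher rows with an HC2 variance; a check on simulated calls gave the same estimate (−0.0084774) and SE (0.0212676) both ways. For RR, each dispatcher's summed residual is scaled by 1/√(1 − leverage). An unweighted dispatcher-level regression is an alternative only if the SAP says that it weights dispatchers, not calls, equally.

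The cost is SAP wording, a covariate already in hand, a stated variance correction and one or two degrees of freedom. If the 2022 share predicts nothing, the interval is 4–5% wider for RD and 11–12% wider for RR. Almost all of that restores coverage to about 95%; the covariate itself costs under 1% (1.4% with looser pairing).

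Section 3.5 reports that data extraction had not begun when the SAP was written. If that is still so, the change can be prespecified.

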3.2 Inclusion-Exclusion Criteria and General Study Population

All emergency calls received at the Emergency Medical Dispatch Center and handled by either the intervention or control group will be included in the study.

Inclusion criteria

- Emergency calls (1-1-2 calls equivalent to 9-1-1 calls),
- Received by an EMS dispatcher included in the study (intervention or control group/cluster).

Exclusion criteria

- All calls to the EMDC other than emergency calls (including those from hospitals and general practitioners, including those outside of regular hours),
- Emergency calls managed by EMS dispatchers who are newly employed within the study period, on long-term leave, or not employed until the end of the study period are excluded from the study,

• Emergency calls managed by technical dispatchers (logistical dispatcher restricted to dispatching only the highest urgency level).

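### Cluster-robust variance on about 20 dispatchers without a small-sample method: mortality and ICU intervals come out modestly too narrow, and for outcomes tied to the matching the direction of error is unknown

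*SAP*

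**What the plan says.** Section 3.6 analyses binary outcomes by linear regression (risk difference, RD) and Poisson regression (relative risk, RR). It adds Cox, Tobit and ordered logistic models for other outcomes. For all of them "we will implement cluster robust variance in all regression analyses with a separate cluster id for each EMS dispatcher". Intervals are 95% and the software is Stata 17. No small-sample correction, reference distribution or degrees of freedom is named, and no pair term appears.

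Section 2.3 divides the dispatchers into "one of two clusters, each containing 10 EMS dispatchers" and gives the small number of clusters as the reason for matching. Matching used "the average proportion of dispatched urgency levels (with the highest urgency level as the primary criterion), years of employment, and the average call duration". It was not complete: "Newly employed personnel where matching was not possible were randomly assigned to one of the two clusters". Section 3.2 then excludes calls handled by dispatchers who are newly employed in the study period, "on long-term leave, or not employed until the end of the study period are excluded from the study".

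Section 2.4 names A-responses as the primary outcome. The secondary outcomes include "Mortality within 30 days after study inclusion" and "The number of participants needing an ICU admission at hospital". Section 3.7 handles missing data by multiple imputation.

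**The concern.** The ordinary cluster-robust variance is justified by a large number of clusters. With about 20 it is biased downwards, more so when call volumes are uneven. A normal reference distribution, if used, narrows the interval further. For outcomes with little relation to the matching, nothing offsets this. Intervals then exclude no effect more often than 5% when there is none, and the RR and RD intervals for the same outcome carry different error rates.

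A second fault acts in the opposite direction. If matching made paired dispatchers alike, an analysis that ignores the pairs overstates the variance of the group difference. This applies to A-responses, the other urgency levels and call duration, which relate directly to the matching criteria. It plausibly applies to readmission after a level E dispatch as well. For these outcomes a reader cannot tell whether the interval is too narrow or too wide, and the primary outcome is among them.

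**Working it through.** **The SAP's own figure.** Sections 2.2 and 2.3 give 120 days and 55,000-60,000 calls a year. 55,000 × 120/365 = 18,082 and 60,000 × 120/365 = 19,726, which agrees with the 18,000-20,000 calls in section 3.4. The 20 study dispatchers out of about 25 would take 18,000 × 20/25 = 14,400 to 20,000 × 20/25 = 16,000 calls. The main simulations use 15,000.

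**Assumptions not in the SAP.** Variance factor G/(G-1); z for Poisson and t on G-1 for linear regression; event risks, dispatcher SDs, spread of call volume (coefficient of variation, CV) and within-pair correlation.

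**Closed form, outcome unrelated to the matching.** Take equal volumes and n = G/2 independent dispatchers per group. The exact reference is the two-sample t on dispatcher means, with factor n/(n-1) and G-2 degrees of freedom. The true error of the planned interval is

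P(|t(G-2)| > crit × √[(G/(G-1)) × ((n-1)/n)]).

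For G = 20 the root is √(20/19 × 9/10) = 0.973.
- RR: 1.960 × 0.973 = 1.908, giving 7.25%.
- RD: 2.093 × 0.973 = 2.037, giving 5.66%.

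| Dispatchers | RR | RD |
|---|---|---|
| 25 | 6.75% | 5.51% |
| 20 | 7.25% | 5.66% |
| 18 | 7.54% | 5.75% |
| 16 | 7.91% | 5.86% |

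**Simulation, same kind of outcome** (20 dispatchers, 15,000 calls, 40,000 replicates, nominal 5%):

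| Risk, dispatcher SD | RR at CV 0 / 0.2 / 0.4 / 0.6 | RD at CV 0 / 0.2 / 0.4 / 0.6 |
|---|---|---|
| 5%, 0 | 7.0 / 7.2 / 7.6 / 8.3% | 5.5 / 5.6 / 5.8 / 6.6% |
| 5%, 1 point | 7.3 / 7.5 / 7.9 / 9.1% | 5.8 / 5.9 / 6.4 / 7.4% |
| 2%, 0 | 7.4 / 7.4 / 7.5 / 8.1% | 5.8 / 5.9 / 6.0 / 6.5% |

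With 16-18 dispatchers (5% risk) the ranges are RR 7.4-9.7% and RD 5.6-7.6%. A simulation with other assumed inputs (risks 4% and 3%, 12,000 or 18,000 calls, 20 dispatchers) gives coverage of 91.6-92.9% for RR and 93.3-94.5% for RD, which agrees.

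**Outcome tied to the matching, pairs ignored** (40% share, dispatcher SD 5 points, CV 0-0.6):

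| Pairs | Within-pair correlation | RR | RD |
|---|---|---|---|
| 10 intact | 0.3 | 3.9-6.2% | 2.9-4.8% |
| 10 intact | 0.6 | 1.4-3.2% | 1.0-2.3% |
| 6 intact, 8 dispatchers per group | 0.3 | 5.3-7.9% | 3.8-6.1% |

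The error lies on either side of 5% depending on inputs the SAP does not give.

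**Candidate repairs.**
- CR3 with t on G-2, outcome unrelated to matching: 4.4-5.1%. CR2 with Satterthwaite degrees of freedom, RD: 4.8-5.6%.
- CR3 without the pairs, matched outcome, 10 pairs: 2.1-3.1% at correlation 0.3 and 0.7-1.4% at 0.6. This is more conservative than before.
- Within-pair differences with t on pairs minus 1: 4.8-5.3% with 6-10 intact pairs.
- RD adjusted for a matching variable carrying all the pair correlation: 6.3-9.8% with ordinary variance, 3.5-4.5% with CR3 and t on G-3.
- Pair indicators with dispatcher ids and ordinary variance: 18-21%. With 10 pairs and S the sum of squared deviations of the pair differences, this variance is (20/19) × S/200 = S/190, while the correct one is S/90. The root of 90/190 is 0.688. Then P(|t(9)| > 1.960 × 0.688) = 21% and P(|t(9)| > 2.093 × 0.688) = 18%.

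**The case against.** The strongest reply is that the firm part is small and rests on assumptions. It covers secondary outcomes only, and the SAP plans estimates with intervals and names no significance test. For RD at equal volumes the excess is under one percentage point. The upper figures (9.1% and 7.4%) need a volume CV of 0.6 together with real dispatcher variation in a 5% risk; at CV 0-0.4 the ranges are RR 7.0-7.9% and RD 5.5-6.4%. Much of the RR excess comes from the assumed z reference: t on G-2 alone brings RR to 5.3-6.2% at CV 0-0.4 and up to 7.2% at 0.6. If mortality itself varied between dispatchers (SD 1 point) and correlated 0.3 within pairs, RR error would be 4.9-5.4% and RD 3.7-4.2% (CV 0-0.3). The count is also uncertain: unmatched staff may be additional to the 10 per group, and the 10 may already reflect the exclusions.

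Most of this stands as a limit on size. It does not remove the point. The SAP fixes the variance method and leaves the reference distribution open, so some default has to be assumed. Even with 25 dispatchers RR error is 6.75%. Uncertainty about within-pair correlation is the reason the primary interval cannot be interpreted with confidence. It is also fair that the Cox, Tobit and ordered logistic models and the imputed analyses were not quantified, and that CR2 and covariate adjustment were checked for RD only.

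**Conclusion.** The concern holds and should be addressed; confidence in its size is medium. With 20 dispatchers and the assumed defaults, 95% intervals for outcomes weakly tied to the matching have true error of 7.0-9.1% (RR) and 5.5-7.4% (RD). For A-responses and other outcomes related to the matching, the simulated error runs from 1.0% to 7.9% across the settings tried, so the direction is unknown and no inflation is claimed. The two faults need a joint repair: correcting only the variance makes matched outcomes more conservative, and adding only the pairs or matching variables makes the intervals too narrow. The treatment of mortality and ICU admission as weakly tied to the matching is itself an assumption. No size is claimed for the time-to-event, censored or ordinal models, or after imputation.

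**What to change.** In section 3.6:
- Specify a bias-reduced cluster variance with small-sample degrees of freedom: CR2 with Satterthwaite degrees of freedom, or CR3/jackknife with t on the number of dispatchers minus 2.
- For A-responses, other urgency levels, call duration and readmission after level E, combine this with the matching. Either analyse within-pair differences with t on pairs minus 1, or adjust for the matching variables with CR2 or CR3. State which group each remaining dispatcher-driven outcome falls in, such as urgency changes during the call and time to dispatch.
- Do not add pair indicators while keeping dispatcher ids with ordinary variance.
- State how unmatched dispatchers and pairs broken by the section 3.2 exclusions enter, and how variance and degrees of freedom are combined across imputations.

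The cost is wording, some code and a change in width. CR3 with t on G-2 and 20 dispatchers widens intervals by 13% (RR) and 6% (RD) at equal volumes, and by 17-19% and 9-11% at CV 0.6. The equal-volume RD figure is (10/9) × √(19/20) × 2.101 / (2.093 × √(20/19)) = 1.06. CR2 for RD costs 3% and 7-8%. Within-pair differences with 10 pairs, against the planned RD interval, are 7-11% wider at correlation 0, 5-7% narrower at 0.3 and 24% narrower at 0.6. They weight pairs equally rather than by calls. Section 3.5 says data extraction had not begun when the SAP was written, so the choice could be fixed before outcomes were seen.
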